### **8.4 Statistical Analysis Process**

The study will be analyzed by the Sponsor (or a nominated designee).

The primary endpoint (proportion who have died or progressed to RF at Day 28) will be analyzed using a logistic regression with treatment group and covariates, age group (50 to <75 years, and > 75 years), baseline WHO ordinal clinical scale (3 or 4), and region. Other covariates including previous COVID-19 therapy may be explored. Estimation of the covariate-

adjusted difference in proportion responding will be reported using Cochran-Mantel-Haenszel (CMH) weighting and estimates from the logistic regression (LR) as described by Ge and colleagues (Ge et al., 2011, Appendix C). This analysis will be repeated without the covariate. Deaths prior to Day 28 will be included in the endpoint (RF, death). WHO Ordinal Scale for COVID-19 scores ([Table 2](#)) will be analyzed by carrying forward any early deaths through Day 28; other categorical and continuous outcomes will be described. The primary analysis will be based on the Intent-to-Treat population (ITT), analyzed as randomized. The denominator for the proportions alive and RF-free at Day 28 will include all randomized subjects. Subjects lacking sufficient data to confirm RF-free and alive at Day 28 will be included in the primary analysis as treatment failures. If more than 5% of subjects have insufficient data to confirm RF-free and alive at Day 28, BioAge will employ a MI strategy (SAS MI, MIANALYZE) based on the patients last known status. For example, the last known WHO Score for a patient lost to follow-up can be used to impute missing primary outcome from patients with known primary outcome and similar WHO Scores. For the primary comparison, analysis by treatment group will be, “as randomized”. Secondary analyses of the primary endpoint may be repeated for the mITT and the per protocol populations, analyzed as treated. Time-to-RF will be analyzed using methods of Kaplan-Meier (KM), with time zero at randomization. Hazard ratios (Cox PHREG) with 95% confidence intervals will describe the treatment effect.

A sensitivity analysis may be completed to assess concurrent treatments and prior SARS-CoV-2 vaccinations in relation to the primary endpoint.

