4.0	14MAR2022	[REDACTED]	Updated per FDA comments dated November 24, 2021 and BioAge response.
5.0	01JUN2022	[REDACTED]	
1. Update on primary endpoint analysis by removing baseline WHO ordinal scale/ Addendum is added for the justification.2. Other minor corrections

1 Introduction

This Statistical Analysis Plan (SAP) contains a more technical and detailed elaboration of the principal features of the analysis described in the protocol and includes detailed procedures for executing the statistical analysis. This SAP should be used in conjunction with the protocol. If there are any discrepancies between the protocol and SAP, this SAP will prevail. Any deviations from this SAP that are implemented in the final analysis will be documented with sound clinical and statistical rationale in the Clinical Study Report (CSR). In the event of any changes to the primary endpoints or analyses, these changes will be documented through a protocol amendment, consistent with ICH E9 Statistical Principles for Clinical Trials.

The SAP is based on protocol v5.0, Amendment 04 dated 07 Sep 2021.

Pharmacokinetics (PK) and pharmacodynamics (PD) analyses and reporting are not included in this analysis plan.

A separate document contains the table, figure and listing specifications and any example programming codes.

2 Study Design

This is a randomized, placebo-controlled, parallel-group, multicenter, double-blind study of asapiprant (BGE-175) administered by oral administration (PO) or through a nasogastric tube (NG) in patients \geq 50 years of age and hospitalized with documented coronavirus disease 2019 (COVID-19) infection who are not yet in respiratory failure (RF).

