If more than 5% of subjects have insufficient data to confirm RF-free and alive at Day 28, BioAge will employ a MI strategy (SAS MI, MIANALYZE) with missing at random (MAR) based protocol stratification factors (age and region), treatment, and the discharge status prior to or on Day 28. Following steps will be followed for multiple imputation.

Step 1: which will be carried out to produce n (exp. 25) imputed datasets

The SAS procedure PROC MI using the FCS (fully conditional specification method) statement with LOGISTIC imputation method to impute RF28 assuming no covariate will be missing.

One must also specify a VAR statement with outcome variable being the last in the order. If any covariate is expected to have missing and need to be imputed as well

`"LOGISTIC (RF28SUB_MI=TRT01P REGION AGEGRN DISC28)"` also need to be added after the FCS statement.

```
PROC MI DATA=RF28 _ DATA SEED=1305417 NIMPUTE=25 OUT=OUTLOG;  
  CLASS RF28 TRT01P REGION AGEGRN DISC28;  
  VAR TRT01P REGION AGEGRN DISC28 RF28;  
  FCS LOGISTIC (RF28SUB_MI=TRT01P REGION AGEGRN DISC28) ;  
RUN;
```

Where:

RF28 is respiratory failure or death prior to or on Day 28

TRT01P is randomized treatment (Placebo/Asapiprant)

REGION: region of patient's location (North America/South America)

AGEGRN: age group (50 - <75, >=75)

DISC28: discharge status prior to or on Day 28

Step 2: Each of 25 complete data set will be analyzed using standard logistic analyses as specified for primary efficacy analysis in SAP, i.e. PROC LOGISTIC will be used for RF28 with predefined covariates (region and age group) and treatment group.

```
PROC LOGISTIC DATA=OUTLOG ;  
  CLASS RF28 TRT01P REGION AGEGRN ;  
  MODEL RF28=TRT01P REGION AGEGRN / COVB;  
  BY IMPUTATION ;  
  ODS OUTPUT PARAMETERESTIMATES=LGSPARMS;  
RUN;
```

Step 3: The results logistic regression from the 25 complete data sets are combined for the parameter inference (i.e. coefficient estimate, 95% confidence interval, and p-value) using PROC MIANALYZE

```
PROC MIANALYZE PARMs=LGSPARMS;  
  MODELEFFECTS INTERCEPT TRT01P REGION AGEGRN;  
RUN;
```

QMS Document Name: Statistical Analysis Plan	Page 19 of 27
QMS No (include version ref): STF-015-GL02	Document date: 09JUL2019
CONFIDENTIAL	

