- 2) based blinded data review, all those subjects who had baseline WHO scale=3 had no respiratory failure, and therefore leading quasi-complete separation on primary endpoint.

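### The SAP narrows the protocol's last-known-status basis for imputing the primary endpoint to discharge status, and so leaves oxygen status out of the imputation model without a stated reason

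*SAP*

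**What the plan says.** Protocol 8.4 states that above 5% missing, "BioAge will employ a MI strategy (SAS MI, MIANALYZE) based on the patients last known status". It then illustrates this: "the last known WHO Score for a patient lost to follow-up can be used to impute missing primary outcome", borrowing from patients with a known outcome and similar scores. The same section leaves further detail on missing data to the SAP.

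SAP 10.1 keeps the trigger ("If more than 5% of subjects have insufficient data to confirm RF-free and alive at Day 28") but specifies a missing-at-random model with age group, region, "treatment, and the discharge status prior to or on Day 28". The code agrees with the text: the variable list is "VAR TRT01P REGION AGEGRN DISC28 RF28", and the imputation statement has the same four predictors. No WHO score appears, baseline or later.

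SAP section 16 (Addendum) reports from blinded review that "all those subjects who had baseline WHO scale=3 had no respiratory failure, and therefore leading quasi-complete separation on primary endpoint". On that ground it takes baseline WHO score out of the primary logistic regression. It does not mention the imputation model.

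SAP section 1 says that the SAP overrides the protocol where they differ. It also says of changes to the primary endpoints or analyses that "these changes will be documented through a protocol amendment". The protocol history ends at version 5.0 (07 September 2021), which still has the last-known-status wording; the current SAP is dated 01 June 2022.

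**The concern.** The imputation assumes that outcomes are missing at random given the variables in the model. Take two inpatients who are lost to follow-up, one off oxygen (score 3) and one on oxygen by mask or prongs (score 4). If they share arm, region, age group and discharge code, they receive the same imputed risk. The trial's own blinded data indicate that the risks differ by baseline score.

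Discharge status may not repair this. The SAP gives no rule for a patient lost while still in hospital. If such a patient is coded as not discharged, the imputation borrows from patients still in hospital at Day 28 or who died there, so even the direction of the error is unclear.

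The stakes are highest where the model is used. On a natural reading, above 5% missing the imputed analysis carries the primary comparison. The four analyses that set missing outcomes to success or failure are specified only at 5% or less, and no sensitivity analysis of the imputation is specified above it. Since SAP version 5.0 the analysis model has no oxygen-status term either.

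**Working it through.** **1. Variables side by side**

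| Source | Basis for imputation |
|---|---|
| Protocol 8.4 | Last known status; last WHO score as an example |
| SAP 10.1, text | Age group, region, treatment, discharge by Day 28 |
| SAP 10.1, code | TRT01P, REGION, AGEGRN, DISC28 |
| SAP 16 | Drops baseline WHO from the analysis model; silent on imputation |

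The narrowing is real and unexplained.

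**2. Event rates for an illustration**

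Protocol 8.6 and SAP 2.2 assume 31% against 15%, a 16-point difference, with 312 patients. That figure reproduces: the continuity-corrected formula gives 156 per arm (312), and exact Fisher power at 156 per arm is 90.5%. It is not in dispute; it only supplies the rates.

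**3. Possible shift in the treatment difference**

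Assumptions, none of them from the documents: a share q of each arm is at WHO 3 with zero risk; a share m of outcomes is missing; a share s of the missing patients is at WHO 3; within a WHO level, loss is unrelated to outcome; discharge status adds no information.

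- Risk at WHO 4: r = p / (1 − q)
- Share at WHO 3 among the observed: o = (q − s·m) / (1 − m)
- Rate after imputation without WHO score: (1 − o) × r

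Example with q = 0.30, m = 0.10 and all missing patients at WHO 4 (s = 0). Then o = 0.30/0.90 = 0.333. Control: 0.667 × 0.31/0.70 = 29.5%. Asapiprant: 0.667 × 0.15/0.70 = 14.3%. The difference is 15.2 points, a shift of −0.8.

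| Missing patients at | q | m | Control | Asapiprant | Difference | Shift |
|---|---|---|---|---|---|---|
| Same mix as the arm (s = q) | any | any | 31.0% | 15.0% | 16.0 | 0 |
| WHO 4 in both arms | 30% | 10% | 29.5% | 14.3% | 15.2 | −0.8 |
| WHO 3 in both arms | 10% | 10% | 34.4% | 16.7% | 17.8 | +1.8 |
| Control WHO 4, asapiprant WHO 3 | 30% | 10% | 29.5% | 16.7% | 12.9 | −3.1 |
| Control WHO 3, asapiprant WHO 4 | 30% | 10% | 34.4% | 14.3% | 20.2 | +4.2 |

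These rows are the extremes over q from 10% to 30% and m of 5% or 10%. At m = 5% the extremes are −0.4 to +0.8 (same pattern) and −1.5 to +2.0 (opposite patterns). A positive shift overstates benefit.

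**4. Can baseline WHO score be added as a plain term?**

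One simulated set (assumed N = 200: 24 at WHO 3 with 0 events; 176 at WHO 4 with 53 events and 123 non-events) was fitted by ordinary logistic regression. The WHO coefficient runs off to −10.8, −25.8 and −36.8 at 10, 25 and 100 iterations, with standard error 37.9 at 10 iterations and about 68,500 at 25. The treatment coefficient stays at −1.47.

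Imputation draws coefficients from their estimated distribution. With −10.8 and standard error 37.9, the ratio is 0.285, so about 39% of draws are positive; with −25.8 and 68,500 it is about half. Zero-risk patients could then be imputed as failures almost at random. The separation has to be handled in the fit.

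**The case against.** Several counter-arguments stand.

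- A reader might infer that the SAP removed a variable that the protocol requires. It did not. The protocol's basis is last known status, and the WHO score is an optional example. Discharge status is itself a coarse status: on the WHO scale, ambulatory patients score 1–2 and hospitalised patients 3–7. The protocol hands missing-data detail to the SAP, so whether the amendment clause applies is arguable.
- A reader might infer from the addendum that the WHO score sorts failures from non-failures. The separation is quasi-complete and one-sided: score 3 had no respiratory failure, while score 4 holds all the respiratory failures and also patients without one. The statement concerns the baseline score, not the last score, and counts respiratory failure, although the endpoint also includes death.
- A reader might size the harm as a count of wrongly imputed failures. With an assumed 8% missing of 312 (25 patients), the average risk of 23% and 10% to 50% of them at WHO 3, this is 25 × 0.10 × 0.23 = 0.6 to 25 × 0.50 × 0.23 = 2.9. That is a gross figure: it is not split by arm, is not netted against errors at score 4, ignores discharge status and uses the design sample size. It does not measure bias in the comparison.
- Patients with respiratory failure recorded before loss already have an outcome, and follow-up continues after study drug stops. Missingness may stay at or below 5%, and then the imputation is not run.
- A raw last WHO score is a poor predictor to add. For completers it lies near Day 28, where scores of 5 and above largely restate the endpoint.

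None of this explains the omission of baseline score. Separation is a fitting problem; it does not show that the score is uninformative, and the addendum's reason concerns another model.

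**Conclusion.** The point holds in a limited form. SAP 10.1 narrows the protocol's basis to discharge status without explanation, and no baseline or pre-dropout oxygen status informs the imputed outcomes, although the SAP itself reports a clear difference in respiratory failure by baseline score.

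The treatment comparison is at risk only if more than 5% of outcomes are missing and loss is related to WHO status, most of all if the relation differs by arm. If loss is unrelated to WHO status, the bias is zero. The real size cannot be determined: the missing rate, the share at score 3 and the actual sample size are not given, and the addendum says that recruitment ended ahead of the interim look, so 312 is only a design figure. The illustrated shifts (up to −0.8 or +1.8 points with the same pattern in both arms, −3.1 or +4.2 with opposite patterns) are extreme patterns under stated assumptions, not estimates. Informative discharge data would change them.

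This is a worthwhile, inexpensive improvement, not a fatal flaw.

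**What to change.** - Add baseline WHO score (3 or 4) to the PROC MI model as an auxiliary predictor beside treatment, region, age group and discharge status. Use an augmented or penalised logistic fit, because score 3 has no respiratory failure events. Leave the analysis model unchanged.
- If the last known WHO score is also used, define it comparably for completers and dropouts, for example as the score at a matched study day, restricted to levels below 5.
- State how discharge status is coded for patients lost while in hospital.
- Make the change before unblinding and reconcile SAP 10.1 with Protocol 8.4, documented as SAP section 1 requires. If the sponsor prefers the present model, give the reason there.
- In the same edit, align the outcome name in the FCS statement (RF28SUB_MI) with the variable list (RF28).

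The cost is small. Baseline score is already collected, and SAP 4.7 has a fallback rule for it. The downside is a slightly more complex imputation step with sparse cells. All enrolled patients have passed Day 28, so the missing rate can be checked blinded first; at 5% or less the change has no effect on the results.

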10.2 Secondary efficacy analyses

All secondary efficacy endpoints will be analyzed without adjustment for multiplicity using ITT and mITT and PPS (if formed) under randomized treatment based on the data observed. No missing data will be imputed unless specified otherwise.

10.2.1 Proportion of binary endpoints

The number and percentage of the following binary endpoints will be presented by treatment and timepoint. Comparison of proportion of patients between treatment at each timepoint will be analysed by the same manner as primary endpoint.

- Proportion of patients who had survived at each timepoint at Day 14, at Day 28, at Day 57: which is defined as patients who had no documented death prior or on timepoint at Day 14, 28, 57.
- Proportion of patients who survive without progression to RF at each timepoint at Day 14, Day 28, Day 57: which is defined as patients who had neither documented death nor respiratory failure prior or on timepoint at Day 14, 28, 57.
- Proportion of patients who had intubation during the study: which will be defined as proportion of patients who had any documented intubation during the study.
- Proportion of patients who develop critical COVID-19 illness as defined by at least one the following:
 - A. Respiratory failure defined based on resource utilization requiring at least one of the following: Endotracheal intubation and mechanical ventilation, oxygen delivered by high-flow nasal cannula (heated, humidified, oxygen delivered via reinforced nasal cannula at flow rates > 20 L/min with fraction of delivered oxygen ≥ 0.5), noninvasive positive pressure ventilation, ECMO clinical diagnosis respiratory failure (i.e., clinical need for one of the preceding therapies, but preceding therapies not able to be administered in setting of resource limitation)
 - B. Hemodynamic compromise (defined by systolic blood pressure < 90 mm Hg, or diastolic blood pressure < 60 mm Hg or requiring vasopressors)
 - C. Multi-organ dysfunction/failure
- Proportion of patients requiring intensive care unit admission: which is defined as patients who had been admitted to intensive care unit during the study.
- Incidence of supplemental O₂ administration: which will be defined as proportion of patients who had any documented post-dosing supplemental O₂ administration during the study.
- Incidence of noninvasive ventilation or high-flow nasal cannula O₂ administration: which will be defined as proportion of patients who had any documented post-dosing noninvasive ventilation or high-flow nasal cannula O₂ administration.
- Incidence of mechanical ventilation: which will be defined as proportion of patients who had any documented post-dosing mechanical ventilation.
- Incidence of mechanical ventilation plus additional organ support using vasopressors, and/or renal replacement therapy and/or ECMO: which will be defined as proportion of patients who had any documented post-dosing mechanical ventilation plus additional organ support using vasopressors, and/or renal replacement therapy and/or ECMO.

QMS Document Name: Statistical Analysis Plan	Page 20 of 27
QMS No (include version ref): STF-015-GL.02	Document date: 09JUL2019
CONFIDENTIAL	

- Incidence of re-hospitalization through Day 57: which will be defined as proportion of patients who are hospitalized again after the discharge of first hospitalization.

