Secondary endpoints that are proportions will be analyzed like the primary endpoint, using logistic regression with and without the designated covariates and by FET. 95% confidence intervals and p-values (without correction) will be presented for these descriptive analyses. Time-to-event analyses will use the methods of Kaplan-Meier with censoring rules for the different endpoints provided in the SAP. Descriptive statistics for TTE will be median times to event with 95 confidence intervals and log-rank statistics to test for treatment differences; Cox proportional hazards with 95% CI will be presented.

“Incidence and duration” secondary endpoints will be analyzed by counting days per subject and then forming 95% confidence intervals and Wilcoxon tests and t-tests to compare treatments. Incidence will also be compared using FET.

These analyses of secondary endpoints will be done using the ITT population and may be repeated for the mITT and PP populations.

No secondary endpoints are designated as, “key” for any labeling purposes.

Results of secondary endpoint analyses will not be corrected for multiplicity.

The Sponsor does not intend formal statistical analyses for safety data. However, odds ratios (95% CI) for common adverse events will be displayed.

The SAP will further describe the statistical methods and definitions for the analysis of the efficacy endpoints, PK, PD, and safety data, as well as describe the approaches to be taken for summarizing other study information, such as subject disposition, demographics and baseline characteristics, IP exposure, and prior and concomitant medications. The SAP will also include further description of how missing and spurious data will be addressed.

To preserve the integrity of the statistical analysis and study conclusions, the SAP will be finalized prior to the IA. Analysis rules and methods for the IA are planned to be the same as the rules and methods for the final analysis.

Unless noted otherwise, all statistical analyses will be performed using SAS® Version 9.3 or later (SAS Institute, Cary, NC 27513).

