10.1 Primary efficacy analysis

The number and percentage of patients who have died or have progressed to RF through Day 28 will be presented by treatment. Hypothesis test comparison of proportion between treatment will be analyzed using a logistic regression with predefined covariates and treatment group. The predefined covariates are region and age group. Other covariates including previous COVID-19 therapy may be explored as exploratory analyses. Estimation of the covariate-adjusted risk difference will be reported using Cochran-Mantel-Haenszel (CMH) weighting and estimates from the logistic regression as described by Ge and colleagues (Ge et al., 2011, Appendix C). Two-sided p-value of global test comparison between active and placebo will be reported. Odds ratio of each covariate and two-sided 95% CI will also be reported. This analysis will be repeated without the covariates.

The denominator for the proportions alive and RF-free at Day 28 will include all randomized subjects.

Time from date of randomization to death or first RF through Day 28, whichever comes first, will also be displayed using the Kaplan-Meier estimator and analyzed using a proportional hazards model analysis with the same covariates. If a patient doesn't have documented death or RF, it will be censored at the Day 28. For subject who discontinued study before Day 28 without documented outcome, it will be censored at the date of discontinuation. This analysis will be repeated without the covariates. Test statistics will be the Hazard Ratio with 95% CIs and p-values. Sensitivity test will be done using a Fishers Exact Test.

Primary endpoint will be analyzed using ITT, mITT, PPS (if formed) analysis set under randomized treatment.

Primary endpoint analysis will be repeated for subgroups as specified [section 4.3](#).

Sensitivity analysis and handling of missing primary endpoint data

If $\leq 5\%$ of subjects lack sufficient data to confirm the primary endpoint, four sensitivity analyses will be performed on logistic regression: 1) treat any missing primary outcomes as successes; 2) replaces

QMS Document Name: Statistical Analysis Plan	Page 18 of 27
QMS No (include version ref): STF-015-GL.02	Document date: 09JUL2019
CONFIDENTIAL	

any missing primary outcomes as failures; 3) missing primary outcome imputed as success for drug and failure for controls; 4) missing primary outcome imputed as failure for drug and success for controls.

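### Read literally, SAP 10.2.1 counts a subject of unknown status as alive and RF-free, whereas protocol 8.4 counts unknown Day 28 status as failure for the complementary primary endpoint

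*SAP*

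**What the plan says.** **Secondary endpoints.** SAP 10.2.1 defines RF-free survival thus: "which is defined as patients who had neither documented death nor respiratory failure prior or on timepoint at Day 14, 28, 57". Survival follows the same pattern: "which is defined as patients who had no documented death prior or on timepoint at Day 14, 28, 57". Neither definition asks for evidence that the subject was seen alive or RF-free at the timepoint.

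**Primary endpoint.** SAP 2.3 makes it death or RF by Day 28, so Day 28 RF-free survival is its complement. Protocol 8.4 requires positive evidence: "Subjects lacking sufficient data to confirm RF-free and alive at Day 28 will be included in the primary analysis as treatment failures". Above 5% missing, protocol 8.4 and SAP 10.1 use multiple imputation (MI). Both put all randomized subjects in the Day 28 denominator.

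**Text that links the two.** SAP 10.2.1 says: "Comparison of proportion of patients between treatment at each timepoint will be analysed by the same manner as primary endpoint". Protocol 8.4 says: "Secondary endpoints that are proportions will be analyzed like the primary endpoint".

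**Text that separates them.** SAP 10.2 says that secondary endpoints are analysed "based on the data observed. No missing data will be imputed unless specified otherwise". SAP section 1 adds: "If there are any discrepancies between the protocol and SAP, this SAP will prevail".

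**SAP 10.1 at 5% missing or less.** It says that "four sensitivity analyses will be performed on logistic regression: 1) treat any missing primary outcomes as successes". Counting missing outcomes as failures is the second of the four. The SAP does not say which rule is the main analysis.

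**The concern.** The two endpoints describe one outcome from opposite sides, but the written tests differ. For the primary, being RF-free must be confirmed. For the secondary, it is enough that nothing was recorded. The same lost subject can therefore be a failure in one table and a success in another.

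The literal definition leaves no value missing, since every subject without a recorded event is already a success. A missing-data rule borrowed from the primary analysis then has nothing to act on. The SAP does not treat unknown status this way elsewhere: its time-to-event analysis of the primary outcome (SAP 10.1) censors subjects who leave before Day 28 without a known outcome.

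At stake are overstated survival and RF-free rates at three timepoints and, at Day 28, possibly two different p-values for one outcome in one report.

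**Working it through.** **Inputs from the documents.** 31% against 15% events, N = 312 at 1:1 (156 per arm), two-sided 5%, Fisher's exact test, 90% power (protocol 8.6, SAP 2.2); MI threshold of 5% (protocol 8.4, SAP 10.1). The documents give no expected missing rate and no final N; the SAP addendum says that enrollment stopped before the interim analysis. Missing counts below are therefore assumptions.

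**1. The plan's own figure.** The two-proportion formula gives 144 per arm uncorrected and 156 with the continuity correction, so 2 × 156 = 312. Exact Fisher power at 156 per arm is 90.5%. The sample size is not in dispute.

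**2. Sum of the two Day 28 proportions.** Assume 24 (asapiprant) and 48 (placebo) recorded events, 72 in all, close to 15% and 31% of 156. Assume 15 subjects of unknown status: 15/312 = 4.8%, just under the MI threshold (0.05 × 312 = 15.6).

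| Reading | Primary event rate | RF-free survival | Sum |
|---|---|---|---|
| Failure rule for both | 87/312 = 27.9% | 225/312 = 72.1% | 100% |
| Recorded events only for both | 72/312 = 23.1% | 240/312 = 76.9% | 100% |
| Protocol 8.4 for primary, SAP 10.2.1 for secondary | 87/312 = 27.9% | 240/312 = 76.9% | 104.8% |

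In the mixed reading the excess is the missing share, k/N. Above 5%, with MI for the primary only, it is the missing share times the imputed event probability: with 10% missing and 23% (the mean of 31% and 15%), 0.10 × 0.23 = 2.3 points.

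**3. Effect on the comparison.** Same counts; Fisher p-values stand in for the adjusted logistic regression. Differences are asapiprant minus placebo in event rate.

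| Rule; unknowns asapiprant/placebo | Events | Difference (points) | Odds ratio | p |
|---|---|---|---|---|
| Literal, any split | 24 vs 48 | −15.4 | 0.41 | 0.002 |
| Failure, 8/7 | 32 vs 55 | −14.7 | 0.47 | 0.005 |
| Failure, 11/4 | 35 vs 52 | −10.9 | 0.58 | 0.043 |
| Failure, 12/3 | 36 vs 51 | −9.6 | 0.62 | 0.077 |
| Failure, 5/10 | 29 vs 58 | −18.6 | 0.39 | 0.0004 |

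Near-equal loss hardly moves the risk difference; the odds ratio moves a little. Unequal loss moves both, in either direction. If each of the 15 is equally likely to come from either arm, Binomial(15, 0.5) gives 5.9% for 11 or more on asapiprant and 1.8% for 12 or more.

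**4. Power under each rule, 5% missing in both arms.** Literal: 0.95 × 15% = 14.25% and 0.95 × 31% = 29.45%, exact Fisher power 88.4%. Failure: add 5 points to each, 19.25% and 34.45%, power 83.5%.

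**The case against.** The best reply is that the documents already carry the primary rule over. SAP 10.2.1 and protocol 8.4 both tie secondary proportions to the primary method, the no-imputation sentence in SAP 10.2 allows exceptions, and SAP precedence applies only where the documents disagree. On this view unknowns are failures in both places and the proportions sum to 100%. Equally, SAP 10.1 taken alone counts recorded events over all randomized subjects, so reading the SAP literally throughout also gives 100%. A sum above 100% needs protocol 8.4 to fill the SAP's silence for the primary while the SAP definition overrides the protocol for the secondary.

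That last point stands, and the 104.8% must be read with that condition. The rest stands in part. The linking sentences concern how arms are compared or proportions analysed; they do not replace an explicit definition of who is a survivor. Both readings remain open, and two programmers could produce different tables. The objection is also right that 15 of 312 lies near the top of the band below the MI threshold, and that missing values at 5% or less expose a gap in SAP 10.1 itself.

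A reader might infer that the plan favours asapiprant, or that the primary analysis lacks a missing-data rule. The documents support neither. The direction depends on which arm loses more subjects, and nothing suggests that it would be placebo or asapiprant. For the primary, protocol 8.4 supplies the failure rule; SAP 10.1 needs a clarifying sentence.

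**Conclusion.** The point holds as a minor defect of definition. SAP 10.2.1, followed as written, credits unknown status as success at every timepoint, which overstates the rates and conflicts with protocol 8.4 for the complementary Day 28 outcome. The overstatement relative to the failure rule equals the missing share: 4.8 points at an assumed 15 of 312. The proportions sum to more than 100% only in the mixed reading. The risk difference changes materially only with unequal loss, and under equal chance of loss the splits that would cross nominal significance here are uncommon (1.8% for 12/3 or worse in that direction).

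No result is shown to be wrong: missing counts are assumed and the final N is not stated. Protocol 8.4 names no secondary endpoint as key and makes no multiplicity correction, so these analyses are descriptive and the harm is limited to inconsistent or flattering descriptive rates.

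**What to change.** 1. **SAP 10.2.1, Day 28 RF-free survival:** define it as the exact complement of the primary endpoint under the same missing-data rule (failure at 5% missing or less, the specified MI above 5%).
2. **SAP 10.2.1, other survival and RF-free timepoints:** require status to be confirmed at the timepoint, so that absence of a record is not a success, and report the number of unknown status by arm. The specified MI should not simply be borrowed here: it models only the Day 28 outcome, using discharge status to Day 28. Because Day 57 is a telephone contact (protocol 7.1.2.2), a missed call would lower the confirmed rate. A Kaplan-Meier estimate, censored at the last date known alive or event-free, may be added as a supportive display but not as a replacement; it assumes that loss is unrelated to outcome.
3. **SAP 10.1:** state that at 5% missing or less the main analysis is the protocol 8.4 failure rule and the other three scenarios are sensitivity analyses.

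The cost is a few sentences and minor programming, best settled while the data are still blinded. Reported rates become slightly less favourable. Power for the Day 28 RF-free comparison is lower than under the literal rule: 83.5% against 88.4% at N = 312 with 5% missing in both arms.
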